1. INTRODUCTION, BACKGROUND & OBJECTIVE

Osteoarthritis or other degenerative changes or injury can cause damage to the structures in the knee, causing pain, discomfort, and lessening the quality of life. Knee replacement, or knee arthroplasty, is a common surgical procedure performed to relieve the pain and disability resulting from osteoarthritis. In general, the surgery consists of replacing the diseased or damaged joint surfaces of the knee with metal and plastic components shaped to allow continued motion of the knee.

Today, over 600,000 patients undergo total knee replacement each year in the United States, a number that is projected to increase greatly over the next 20 years (Kurtz 2007). Total knee replacement has been performed since 1964 and has been shown to be an effective, long-lasting procedure with good survivorship of the implants for patients with osteoarthritis. Despite the excellent survivorship, there are still a significant percentage of patients that remain dissatisfied with their results. Studies reveal that 14- 39% of patients report some level of dissatisfaction with their knees post-surgery (Noble 2006; Bourne 2010; Suda 2010).

This study is designed to compare outcome data for patients undergoing surgery with the iTotal® Cruciate Retaining (CR) Knee Replacement System (KRS) versus those who are undergoing surgery with Off-the-Shelf (OTS) systems.

To compare outcomes of these two study groups, this study will include the routine office questionnaires such as the 2011 Knee Society Knee Scoring System © (KSS) and the Knee Injury and Osteoarthritis Outcome Score (KOOS). However, literature suggests that these questionnaires fail to capture the change in functional activities post total knee replacement (Mizner 2010). It has been noted that patients “dramatically overestimate their functional ability early after surgery” (Mizner 2010). The Mizner study showed that there was an increased use in assistive devices and a decrease in functional testing scores post-surgery, while the patient reported outcome scores failed to show worsening. To capture these changes, this study will also conduct multiple functional tests on all patients pre- and post-surgery.

The functional tests used in this study are commonly used as an objective method to assess patients’ functional status. The testing is designed to closely mimic daily activities that the patients are familiar with. In this study, the patient will have a pre-operative visit to serve as a baseline, and then will be retested at predefined post-operative intervals. The patient will perform the same group of functional tests pre- and post-operatively using methods that are summarized below in section 4 and in Appendix B.

2. DEVICE DESCRIPTION

The iTotal CR Knee Replacement System (hereafter referred to as the "iTotal CR") is a patient-specific tricompartmental faceted posterior cruciate ligament (PCL) retaining knee replacement system. The iTotal CR is a semi-constrained cemented knee implant which consists of a femoral, tibial and patellar component.

Using computed tomography (CT) and a combination of proprietary and off-the-shelf software a patient-specific implant is designed, that best meets the geometric and anatomic requirements of the specific patient. The femoral component is manufactured from cobalt chromium molybdenum

("CoCrMo") alloy. The tibial component includes a metal tray manufactured from CoCrMo alloy and polyethylene inserts. The polyethylene inserts may be manufactured from either UHMWPE or a highly cross-linked Vitamin E infused polyethylene (iPoly XE™). The patellar component is also manufactured from either UHMWPE or from a highly cross-linked Vitamin E infused polyethylene (iPoly XE).

Several key features of the iTotal CR are listed below:

- Disposable, patient-specific instrumentation
- Simple, reproducible surgical technique
- Potential for less post-operative pain and shorter post-operative recovery time

The control will be one of three off-the-shelf CR systems:

- DePuy Synthes: Attune
- Zimmer: Persona
- Stryker: Triathlon

For all procedures, the patella will be resurfaced using the patella implant available through the respective manufacturer.

3. STUDY DESIGN

This is a prospective, blinded, multi-center study that will be conducted in the US, UK, and Germany. The study will include a minimum of 450 and a maximum of 600 subjects across up to 20 sites with up to 225 min- 300 max subjects in the iTotal CR arm and 225 min- 300 max subjects in the off-the-shelf total knee arm. An additional 25% may be enrolled to account for subject discontinuation.

Subjects will be consecutively recruited in groups of 10, alternating between study arms until enrollment is completed. Once a series of 10 is recruited (subject signed consent and completed pre-op questionnaires), then the next series of 10 is to be recruited.

To ensure that enrollment in each arm remains relatively even, sites assigned odd site numbers will begin by enrolling off-the-shelf subjects and even numbered sites will begin by enrolling ConforMIS subjects. Subjects will be implanted with either an iTotal CR or an off-the-shelf cruciate retaining total knee replacement.

The person administering the functional tests will be blinded. The blind will be maintained for at least one year in order to maintain an objective assessment of each patient's function. Investigators and study staff will make every attempt to maintain the blind by limiting access to study data, x-rays, and other evaluations.

For all surgeries, the preferred surgical approach is to make an incision that is midline or slightly medial to midline, followed by a parapatellar arthrotomy, or a subvastus arthrotomy with prior written approval from Sponsor. The surgeon must use the same approach for all study subjects.

For surgical technique, the off-the-shelf goal is to obtain mechanical alignment.

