10. ENROLLMENT

Potential subjects will be identified by the Investigator or study staff based on patients' clinical and radiographic assessments during regular medical care. The Investigator or study staff will provide study information and the approved Informed Consent Form to all eligible subjects, (determined via Inclusion/Exclusion criteria), as well as answer any questions about the study.

Once the consent form is signed, the subjects will be assigned a unique subject identification number through the EDC system. Once they complete the first set of pre-operative questionnaires, they will be assigned to one of two treatment arms: A) Treatment with the iTotal CR or B) Treatment with an off-the-shelf knee replacement. The site will be instructed to consecutively enroll 10 subjects per treatment arm, alternating between each arm, until enrollment is completed.

The subject identification number will be comprised of a five digit number starting with a two digit site number assigned by ConforMIS at the Site Initiation followed by a three digit subject number, assigned chronologically for the entire study. For example, at site 01, the first subject enrolled will receive number 01-001, followed by 01-002, 01-003, etc.

The Investigator and/or study staff will assess the subject against the Inclusion and Exclusion criteria to determine eligibility. Eligibility includes clinical assessments, radiographic assessments, and a review of the subject's medical history. The radiographic assessments should include:

1. Knee x-ray: 3 views – AP, lateral, sunrise or Merchant
2. Three foot standing x-ray (full length, full weight-bearing film): AP view

If the subject is not eligible to participate in the study, the subject will not be enrolled and is considered a screen failure. All screen failures will be tracked by the site manually in a tracking spreadsheet and electronically in a clinical database. Subject identification numbers for screen failures will not be re-used.

The following Case Report Forms will be completed for all screen failures:

- SUBJECT INFORMATION/MEDICAL HISTORY
- INCUSION/EXCLUSION CRITERIA

If the subject is eligible to participate in the study, they will be assigned to a treatment arm and will be considered enrolled when they are implanted with a device.

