15. STATISTICAL METHODS

All statistical processing will be performed using SAS® Version 9.3 or later unless otherwise stated.

For continuous variables, descriptive statistics will include n (number of subjects), mean, standard deviation (SD), median, minimum, and maximum. For categorical variables, the number and percentage of subjects in each category will be presented. Appropriate inferential statistics will be used for the primary and secondary efficacy variables.

Populations

The safety population will be comprised of all subjects for whom the procedure is initiated.

The Full Analysis Set (FAS) will be comprised of all subjects for whom the procedure is completed.

The Per-Protocol (PP) population will include all subjects in the FAS who complete the 1 Year visit without significant protocol violations. The PP population will not include subjects who meet any of the following criteria:

- Violated inclusion/exclusion criteria, without sponsor waiver;
- Did not attend the 1 Year visit
- Out of window at the 1 Year visit by +/- 2 months
- Have undergone a procedure to the contralateral knee which may impact the follow-up assessments

Additional criteria may be added to the list to accommodate for unforeseen events that occur during the conduct of the study that impact efficacy assessments. The PP population will be determined prior to data base lock.

Demographic and Baseline Characteristics

Demographic variables (e.g. age, gender, ethnicity, race) and baseline characteristics will be recorded in the CRF. For continuous variables, comparisons between treatment groups will be

conducted with an analysis of variance (ANOVA). A Cochran-Mantel-Haenszel (CMH) test will be used for testing categorical variables.

Efficacy Analysis

Primary Efficacy Analysis

The absolute change from baseline to 1 Year for each primary endpoint will be analyzed using an analysis of covariance (ANCOVA) with factor of treatment (iTTotal CR, OTS) and the respective baseline score as a covariate. The least squares means will be presented along with the observed means.

Secondary Efficacy Analyses

Secondary endpoints will be analyzed as follows:

- The absolute change from baseline to 1 Year for each subscale of KSS will be analyzed using an analysis of covariance (ANCOVA) with factor of treatment (iTTotal CR, OTS) and the respective baseline score as a covariate. The least squares means will be presented along with the observed means.

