- The absolute change from baseline to 1 Year for each subscale of KOOS will be analyzed using an analysis of covariance (ANCOVA) with factor of treatment (iTTotal CR, OTS) and the respective baseline score as a covariate. The least squares means will be presented along with the observed means.
- Post-operative limb alignment will be dichotomized as in and out of “safe zone” (+/- 3 degrees neutral mechanical axis alignment). The proportion of subjects in each study arm summarized and compared using a CMH test.

Safety Analysis

Procedure-related and device-related adverse events (AEs) occurring during the study will be recorded. For the safety population, AEs will be summarized by study arm, the number of subjects reporting AEs, severity, relationship to procedure, relationship to device, and seriousness.

In addition to overall AE summaries, AEs will be summarized for the following study periods:

- Day of procedure to 6 months post procedure
- Annual summaries (1 Year, 2 Year, etc.) from day of procedure

All serious adverse events (SAEs) will be summarized by study arm, severity, relationship to procedure, and relationship to device. SAEs will also be listed by subject.

All information pertaining to AEs noted during the study will be listed by subject.

The Fisher’s Exact test will be used to compare the proportion of subjects in each study arm who have the following:

- procedure-related AEs
- device-related AEs
- revision procedures

Missing Efficacy Data Imputation

The last observation carried forward (LOCF) method will be used to impute missing efficacy data.

Sample Size Determination

A total sample size of a minimum of 450 and a maximum of 600 subjects will be prospectively enrolled in a consecutive fashion, to each arm of the study (approximately 225-300 in the iTotal CR arm and 225-300 in the OTS arm). To ensure that enrollment in each arm remains relatively even, sites assigned odd site numbers will begin by enrolling off-the-shelf subjects and even numbered sites will begin by enrolling ConforMIS subjects. Based on data from a previous study, it is expected that a minimum of 450 and a maximum of 600 total subjects will provide greater than 80% power for the primary functional endpoint.

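### The ANCOVAs for ALF, KSS and KOOS ignore allocation by alternating series of 10 within a site, so their standard errors may be wrong in either direction, and the power figure shows no allowance for it

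*Combined protocol and SAP*

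**What the plan says.** Section 3 (Study Design) allocates by series: "Subjects will be consecutively recruited in groups of 10, alternating between study arms until enrollment is completed". Section 10 (Enrollment) gives this as an instruction to each site: "The site will be instructed to consecutively enroll 10 subjects per treatment arm, alternating between each arm, until enrollment is completed". The starting arm follows from the site number: "sites assigned odd site numbers will begin by enrolling off-the-shelf subjects and even numbered sites will begin by enrolling ConforMIS subjects". On size, Section 3 says "The study will include a minimum of 450 and a maximum of 600 subjects across up to 20 sites", and Section 15 (Sample Size Determination) splits this as "approximately 225-300 in the iTotal CR arm and 225-300 in the OTS arm".

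Section 15 analyses the one-year change in each primary endpoint, and in each KSS and KOOS subscale, by "analysis of covariance (ANCOVA) with factor of treatment (iTTotal CR, OTS) and the respective baseline score as a covariate". No term for site, surgeon or series appears anywhere in the document, nor any random effect or cluster-robust variance. Limb alignment is compared by a CMH test with no stratification factor named.

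On power, Section 15 cites an unnamed previous study and states that "it is expected that a minimum of 450 and a maximum of 600 total subjects will provide greater than 80% power". It gives no effect size, standard deviation, significance level, sidedness, intraclass correlation or design effect.

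**The concern.** The units assigned to an arm are about 45 to 60 series (450/10 to 600/10), not 450 to 600 individuals. Patients in one series share a site and a recruitment window. The primary endpoint also leaves room for local differences. ALF sums raw times, Section 5 asks only for a staircase of at least four steps, and Appendix B asks for the same flight for everyone only where possible. If staircase, tester or care pathway changes over time at a site, the change can fall on a whole series and therefore on one arm.

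An ANCOVA with treatment and baseline score takes patients as independent given baseline. If they are not, the p-value and confidence interval for the primary comparison are miscalibrated. The same dependence would affect the power claim, in which no allowance for it is visible.

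**Working it through.** **Inputs.** From the documents: series of 10, alternating within site, starting arm by odd or even site number; 450 to 600 patients; up to 20 sites; about 1:1. Assumed, because not given: two-sided 5% level; series correlation r and site correlation s, both on the baseline-adjusted scale with total variance set to 1.

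**1. The plan's own power figure.** It cannot be reproduced without an effect size and SD. Inverting it, 80% power needs a standardised difference of (1.960 + 0.842) × √(2/n). That is 2.802 × √(2/225) = 0.264 at 225 per arm and 2.802 × √(2/300) = 0.229 at 300 per arm.

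**2. Series effect only, series independent of each other.** Design effect DE = 1 + (10 − 1) × r. Actual type I error of the planned test = 2 × [1 − Φ(1.960/√DE)]. Power, if exactly 80% under independence, = Φ(2.802/√DE − 1.960). For r = 0.02: DE = 1.18; type I error = 2 × [1 − Φ(1.804)] = 7.1%; power = Φ(2.579 − 1.960) = 73.2%.

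| r (assumed) | DE | Type I error | 450 patients act as | Power if 80% under independence |
|---|---|---|---|---|
| 0.01 | 1.09 | 6.0% | 413 | 76.5% |
| 0.02 | 1.18 | 7.1% | 381 | 73.2% |
| 0.05 | 1.45 | 10.4% | 310 | 64.3% |

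**3. Site and series effects together.** Because arms alternate within a site, the site effect cancels from the arm difference only when a site's arms are equal. To a close approximation, (true SE / model SE)² = 1 + c × s + 9 × r, where c depends on the layout.

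- *15 sites of 40* (four series, 20:20 in each site): the site effect cancels, so c = −1.
- *20 sites of 30* (three series, 20:10 in each site, 300 per arm overall): each site leaves an imbalance of 10/300. The site contribution relative to 2/300 is 20 × (10/300)² / (2/300) = 3.33, so c = 3.33 − 1 = 2.33.

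The approximation gives 1 − 0.05 = 0.95 (SE ratio 0.97) for balanced sites with s = 0.05 and r = 0. It gives 1 + 0.117 + 0.18 = 1.297 (SE ratio 1.14) for 20 sites of 30 with s = 0.05 and r = 0.02. Exact variance calculations agree closely:

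| Layout | s | r | SE ratio | Type I error |
|---|---|---|---|---|
| 40 per site | 0.05 | 0 | 0.98 | 4.5% |
| 40 per site | 0.10 | 0.01 | 1.00 | 5.0% |
| 40 per site | 0.05 | 0.02 | 1.07 | 6.6% |
| 20 sites of 30 | 0.05 | 0 | 1.06 | 6.4% |
| 20 sites of 30 | 0.05 | 0.02 | 1.14 | 8.6% |
| 20 sites of 30 | 0.10 | 0.01 | 1.15 | 8.9% |

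The odd/even starting rule balances the totals across sites, but not the arms within a site that closes after three series.

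**4. Power once site and series are modelled.** At the effect that gives 80% under independence, power is 80.4% (40 per site, s = 0.10, r = 0.01), 75.0% (40 per site, s = 0.05, r = 0.02) and 72.3% (20 sites of 30, same correlations).

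**The case against.** A reader might infer that the planned standard errors are too small. The documents do not establish this. They give no correlation, and most of what a series shares (surgeon, tester, stairs, care pathway) belongs to the site rather than to the series. Section 3 holds each surgeon to one approach, and nothing says that testers or pathways change between series. A pure site effect in a balanced site makes the planned SE slightly too large. This objection stands, so the direction is conditional.

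The design effect in step 2 also treats each series as an independent draw. Adjacent series at a site are in opposite arms. A series closes at consent and pre-operative questionnaires, up to four months before surgery, so operation and assessment dates of neighbouring series can overlap. Under slow calendar drift, neighbouring series then partly cancel. With exponentially decaying drift over 20 to 50 patients (an assumption), scaled to the same average within-series correlation, type I error is about 5.0% to 5.6% at 0.02 and 5.0% to 6.5% at 0.05. Faster decay, over 5 to 10 patients, gives 5.5% to 6.5% and 6.3% to 8.8%. This stands too: 7% and 10% are the less favourable end of the range.

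A reader might also infer that the power is overstated. The text claims more than 80% without inputs. With an assumed standardised difference of 0.30, power at 225 per arm is 88.9%, and still 83.4% at a design effect of 1.18. At 300 per arm it is 86.2% even at 1.45. Missing inputs make the claim unverifiable, not false.

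Finally, the point does not extend to every efficacy analysis. For limb alignment, the CMH strata are simply unstated.

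None of this removes the mismatch between the allocation unit and the ANCOVAs.

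**Conclusion.** The point holds in conditional form. Allocation is by series within site, and the ANCOVAs for ALF, KSS and KOOS contain nothing that reflects it. Their type I error could lie anywhere from about 4.5% (balanced sites, site effect only) to about 10% (series correlation 0.05, or three series per site with moderate site and series effects). Inflation is the likelier direction if sites stop at about 30 patients, which is the average with 600 patients at 20 sites, or if conditions change between series. Every one of these figures rests on assumed correlations.

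The power claim shows no allowance for allocation by series. The fall to about 77% to 64% applies only if power was exactly 80% under independence.

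The correction is cheap and concerns the primary comparison, so it is worth making. With direction and size unproven, I rate it below a must-fix, with moderate confidence in the size of the effect.

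**What to change.** In Section 15, before database lock:

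- Analyse ALF, KSS and KOOS by a linear mixed ANCOVA with treatment and baseline score as fixed effects, site and series-within-site as random effects, and Kenward-Roger degrees of freedom. This corrects the SE in either direction. A site term alone is not a safe substitute: with independent series effects of 0.02 and 20 sites of 30, it still leaves a type I error of 7.2% to 7.5%.
- Store the series number or the order of arm assignment in the EDC. Under Section 10, subject numbers are issued at consent, before the arm is assigned, and numbers of screen failures are not re-used, so the subject number alone does not identify the series.
- Restate the power with effect size, SD, significance level and sidedness, and show it over a stated range of correlations using the design effect.

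The cost is SAP wording and one stored variable, with no new patients or assessments. The interval may be slightly wider and the stated power slightly lower. Settling the model now avoids a variance model chosen after the results are known. The change does nothing about bias from predictable, non-random allocation, which is a separate matter.

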9. SITE SELECTION

All sites will be selected by a Site Selection Committee based on a set of defined criteria. The Site Selection Committee will be led by Clinical Affairs. The site selection criteria includes but is not limited to:

- Interest in participating in the study as demonstrated by responsiveness
- Demonstrated technical and surgical skills with iTotal CR device - Investigator must have completed a cadaver training at minimum prior to enrolling their first subject
- Sufficient patient volume to expect timely subject enrollment
- Ability to adhere to the standards of Good Clinical Practice (GCP) and Good Documentation Practice (GDP)
- Clinical study experience and resources that demonstrate good compliance with study requirements and timely, complete documentation of subject follow-up
- Willingness to allow personnel from ConforMIS (or its designate) access to the hospital records, Investigator's study records, data and patient files as they pertain to the study

During the study, an oversight committee comprised of three individuals: the Lead Study Principle Investigator in the U.S., a second study investigator, and a statistician will review site

performance and data integrity. This committee will determine if the data collected is consistent with the cohort, and meets the minimum enrollment threshold for the study.

If a site has not enrolled a minimum of 20 subjects into the study, data may be excluded from analysis. Likewise, if data quality is inadequate or data is incomplete, the committee may exclude a site's data.

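### At each site the opening arm gets 0 to 10 more recruits than the other, a sponsor-assigned site number decides which arm opens, and the primary analysis does not adjust for site

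*Combined protocol and SAP*

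**What the plan says.** Section 3 (Study Design) sets the recruitment pattern: "Subjects will be consecutively recruited in groups of 10, alternating between study arms until enrollment is completed". To keep the two arms close in size, "sites assigned odd site numbers will begin by enrolling off-the-shelf subjects and even numbered sites will begin by enrolling ConforMIS subjects". Section 10 (Enrollment) describes a subject identifier "starting with a two digit site number assigned by ConforMIS at the Site Initiation". Neither section says that site numbers follow activation order or are drawn by chance.

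On size, Section 3 states: "The study will include a minimum of 450 and a maximum of 600 subjects across up to 20 sites", and adds: "An additional 25% may be enrolled to account for subject discontinuation". Section 15 (Statistical Methods) plans equal arms overall, "approximately 225-300 in the iTotal CR arm and 225-300 in the OTS arm". Section 9 (Site Selection) gives a lower bound for a site: "If a site has not enrolled a minimum of 20 subjects into the study, data may be excluded from analysis". No section caps a site's recruitment or requires a site to finish a pair of series before it closes.

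The primary analysis in Section 15 is an "analysis of covariance (ANCOVA) with factor of treatment (iTTotal CR, OTS) and the respective baseline score as a covariate". Site is not in the model.

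**The concern.** The odd/even rule balances arms across the study, not within a site. Whenever a site stops at a total that is not a multiple of 20, its opening arm is over-represented there. All odd sites lean towards off-the-shelf and all even sites towards iTotal CR. If the two groups of sites differ in mean ALF change, part of that difference is read as a treatment effect, and equal arm totals will not reveal it.

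Sites have reasons to differ. They lie in three countries, and the control is one of three systems. Under Section 5 the stair test needs only 4 steps although 12 is described as usual, and Appendix B asks for the same flight for all subjects only if possible. ALF sums times, so the length of the staircase affects the scale of the score and of its change. The baseline covariate removes some of this, but not necessarily all.

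The opening arm's excess is never negative. The party that assigns the number therefore knows which arm will be favoured at a site, though not by how much.

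**Working it through.** **Plan's own figure.** Section 15 claims more than 80% power but gives no effect size, SD, alpha or sidedness, so the claim cannot be reproduced. Assuming two-sided 5%, the difference detectable with 80% power is 2.80 × √(2/n per arm): 0.264 SD at 225 per arm and 0.229 SD at 300. The point below does not depend on these values.

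**Site sizes.** At 20 sites the average is 450/20 = 22.5 to 600/20 = 30. With the extra 25% it is 562.5/20 = 28.1 to 750/20 = 37.5. With 15 sites, 600/15 = 40.

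**Split within a site.** Let a be the number in the opening arm, b the number in the other arm, and n = a + b. Counting alternating series of 10 for every n from 1 to 199 gives an excess a − b between 0 and 10. With equal-sized sites, half odd and half even, the unadjusted treatment difference contains (a − b)/n times the difference between even-site and odd-site means. The information kept when site is adjusted for is 4ab/n².

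| n per site | a : b | Share entering, (a − b)/n | Information kept, 4ab/n² |
|---|---|---|---|
| 20 | 10 : 10 | 0 | 1.000 |
| 25 | 15 : 10 | 0.200 | 0.960 |
| 28 | 18 : 10 | 0.286 | 0.918 |
| 30 | 20 : 10 | 0.333 | 0.889 |
| 37.5 (average) | 20 : 17.5 | 0.067 | 0.996 |
| 40 | 20 : 20 | 0 | 1.000 |
| 50 | 30 : 20 | 0.200 | 0.960 |

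At 20 sites of 30, ten odd and ten even, each arm has 10 × 20 + 10 × 10 = 300. The totals are exactly even while every site is 2:1.

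**Effect on type I error.** Assume total variance 1, S sites, N = S × n subjects, a site ICC that remains after baseline adjustment, and site numbers unrelated to outcome. The true variance of the unadjusted difference is (1 − ICC) × 4/N + ICC × ((a − b)/n)² × 4/S. The analysis takes it to be about 4/N. The ratio is

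1 − ICC + ICC × (a − b)²/n.

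- At 30 per site, (a − b)²/n = 100/30 = 3.33. The ratio is 1.023, 1.117 and 1.233 for ICC 0.01, 0.05 and 0.10, and type I error is 5.3%, 6.4% and 7.8%. Simulation (20,000 trials, 20 sites) gave 5.2%, 6.4% and 8.0%.
- At 25 per site, (a − b)²/n = 25/25 = 1, so the ratio is 1 and the error is 5%.
- From 20 to 24 per site the ratio is below 1 and the error is below 5%.

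**With site in the model.** Simulated type I error at 20 sites of 30 is 4.6% to 5.2%. The information lost is 1 − 0.889 = 11%, so 600 subjects act like 600 × 0.889 = 533. If the true effect were 0.264 SD (assumption), power at 300 per arm would fall from 89.9% to 86.2%, before any gain from removing between-site variance.

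**The case against.** The strongest reply is that the mixing is partial and often negligible. Every site above 10 subjects has both arms, sites below 20 may be excluded, and at 20 or 40 per site nothing enters. The plan fixes neither the number of sites nor their size, and 30 is the worst ratio for any site that meets the 20-subject minimum. A site term would remove the bias, and the information then lost still leaves 533 effective subjects, above the 450 that the plan considers sufficient. All of this stands, and it is why the point is minor.

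Three stronger readings are tempting, and the documents do not support them:

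- *That 30 per site is a ceiling in the plan.* It is only the average at 600 subjects over 20 sites. Sites may be larger, and the imbalance is then usually milder.
- *That a large share of the detectable effect could be bias.* An even/odd gap of 0.3 SD would give 0.3 × 0.333 = 0.10 SD, or 44% of 0.229 SD. Nothing in the documents supports 0.3 SD. If site numbers are unrelated to outcome, the gap over 20 sites has SD √(4/20) = 0.447 times the between-site SD: about 0.10 SD at ICC 0.05 and 0.14 SD at ICC 0.10. A gap of 0.3 SD would be two to three standard deviations out.
- *That the sponsor steers the comparison through numbering.* The plan says only that the sponsor assigns the number at site initiation. That leaves discretion open but does not show that it is used.

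What remains is that the direction of imbalance at a site is known in advance, no stopping rule limits it, and the primary model ignores it.

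**Conclusion.** The point holds as a modest, avoidable weakness. The opening arm has 0 to 10 more recruits at each site, the parity of a sponsor-assigned number decides which arm that is, and the primary ANCOVA lets part of any even/odd site difference into the treatment effect. That part runs from none (20 or 40 per site) to one third (30 per site). Two-sided 5% type I error rises to about 5% to 8% in that worst case and is at most 5% at 20 to 25 per site.

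These figures assume 20 equal sites, half odd and half even, site numbers unrelated to outcome, and a residual ICC of 0.01 to 0.10. The plan gives neither an ICC nor an alpha. The 10-subject bound applies to recruited subjects: Section 3 counts a series at consent and questionnaires, Section 10 counts enrollment at implantation, and losses in between can change the analysed split. The predictable, non-random assignment of subjects to arms is a separate issue and is not judged here.

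**What to change.** 1. **Section 3, opening arm.** For each site not yet opened, the study statistician draws the opening arm at random, in equal numbers, and it is no longer tied to the sponsor-assigned site number. Sites already open keep their arm. The cost is one paragraph and a short list.
2. **Section 3, site closure.** As a target where recruitment allows, close sites after complete pairs of series (20, 40, ...) within the 450 to 600 total. With 20 sites this needs a mix: all at 20 gives 400, all at 40 gives 800, and 400 + 20k lies within 450 to 600 for k = 3 to 10 sites at 40. Some sites would stop up to 10 subjects earlier or later, which is a third of recruitment for a site at 30. This is why it should be a target and not a rule. It also helps the safety comparisons by Fisher's exact test, which carry no site adjustment.
3. **Reporting.** Give arm counts by site for recruited and for implanted subjects.
4. **Section 15, primary model.** Because the target cannot guarantee balance, add site to the primary ANCOVA. This removes the remaining between-site bias and costs at most 11% of the information, at 20:10, for sites of 20 or more. A site with one arm only adds nothing to a site-adjusted comparison, so state beforehand how small sites are pooled.
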